4.2. Scientific Rationale for Study Design

In this study, all participants will receive PF-07209960. No reproductive or developmental toxicity studies have been performed. Based on the mechanism of action, the risk of teratogenicity is considered possible while there is no risk of clinically relevant genotoxicity or transmission of drug via ejaculate. Therefore, the use of a highly effective method of contraception is required (see [Appendix 4](#), [Section 10.4.2](#) and [Section 10.4.3](#)).

Participants may be asked to provide image-guided core needle biopsies at baseline and during treatment. When on-treatment biopsies are compared to baseline specimens, this information will enable the study of target engagement, optimal biologic dosing, and other genomic and translational markers of interest. Pre-treatment specimens to be collected from all patients as archival tissue and/or fresh tumor biopsies will enable study of baseline tumor markers that correlate with clinical outcomes.

Tumor imaging will be carried out at a rate that is within the standard frequency for Phase 1 oncology trials in solid tumors (every 8 weeks).

Banked Biospecimens will be collected and stored for further analyses which may, for example, provide greater understanding of the study intervention.

4.3. Justification for Dose

Doses presented are projected based on nonclinical data and may be modified based on emerging safety, tolerability, and PK data.

4.3.1. Starting Dose

4.3.1.1. Subcutaneous Dosing

The selection of the starting dose and regimen for this FIH study was based on the nonclinical toxicology and PK results, which are in accordance with the ICH S9 Guidance (ICH S9 Guideline, 2009) for the intended population. For biopharmaceuticals with immune agonist properties such as PF-07209960, selection of the FIH starting dose using a MABEL should be considered. Saber et al., concluded that the FIH doses based on 20% to 80% pharmacology activity from the most sensitive assays had acceptable/manageable toxicities for immune activating antibodies except CD3 specific constructs (Saber et al, 2016; Saber et al, 2017). A dosing was derived based on the a at the projected CCI

in in vitro pharmacology cell (hPBMC) assays.

The projected C_{max} at this MABEL starting dose is also about CCI in vitro pharmacology cell (hPBMC) assay. In addition, the projected C_{max} at this MABEL starting dose is at CCI

In addition to the MABEL approach, calculation of the starting dose based on 1/6 of the HINSTD from the definitive GLP toxicology study in monkeys was also considered. The determined 2W dosing schedule), which corresponds to a FIH interspecies scaling of the animal doses to an equivalent human dose based on normalization to body surface area (SC).

Therefore, the HINSTD derived dose for PF-07209960 would be lower compared to the MABEL derived dose. As a result, CCI

starting dose for PF-07209960.

The fixed-dose approach was chosen as it has been shown to provide similar PK variability compared to a body-weight adjusted dosing for monoclonal antibodies, therapeutic peptides, and proteins (Wang et al, 2009; Zhang et al, 2012). In addition, fixed dosing offers ease of preparation and less chance of dosing errors.

4.3.1.2. Alternative IV Dosing

Based on the available emerging clinical data (including safety/tolerability, PK, PD) from the dose escalation cohorts with SC Q2W administration, IV infusion Q2W administration may be explored in successive dose cohorts. If IV administration is introduced, PF-07209960 will be administered over 1 hour (± 10 minutes) without adjustment for body size at every cycle as indicated in the IP manual. In case of change of the dosing regimen, DLT data accumulated during the dose escalation with the previously explored regimen may be used to inform a prior distribution for new BLRM parameters.

If the IV route is evaluated, there will also be a minimum 72-hour interval between the first dose administered to each of the initial 2 participants (ie, participants contributing to initial DLT evaluation) enrolled at a new dose level to allow the detection of possible infusion

reactions or possible CRS. The participants will be monitored during and following their first dose with at least a 72-hour inpatient hospitalization period. This will be implemented throughout dose escalation and length of inpatient hospitalization will be re-assessed based on safety data prior to starting dose expansion cohorts. Participants should remain at the investigational site for observation for at least 1-hour post dose for all treatment visits after C1D1. Additional inpatient observation for subsequent cycles beyond C1D1 may be considered based on the investigator's discretion and should be discussed with sponsor.

As described in [Section 4.3.1.1](#), the SC starting dose is 1.1 mg SC (rounded to 1 mg). The corresponding IV [CCI](#) the projected exposure associated with the IV dose lower than the projected exposure associated with SC dosing (Table 1).

Table 1. Projected Exposure After SC and IV Dosing

Human Dose	Cmax (μ g/ml)	AUC (μ g*hr/mL)
CCI		

The C_{max} after IV dosing was calculated by the dose divided by the human plasma volume (2.8 L); the C_{max} and AUC in human after SC, and the AUC after IV dosing were derived from the projected human PK profile extrapolated from monkey PK.

The following scenarios would be used to determine the IV starting dose:

Scenario 1: during the course of the clinical study, if the observed exposure at the highest safe/tolerable tested SC dose is higher than that of the projected exposure of the FIH starting SC dose, the IV starting dose will be adjusted using the same principle as described above to ensure the exposure of the IV starting dose does not exceed the exposure of the highest observed clinical safe/tolerable SC dose.

Scenario 2: if the observed exposure at the highest safe/tolerable tested SC dose is lower than that of the projected exposure of the SC starting dose due to unexpectedly low bioavailability in human (bioavailability of 60% is assumed in the human PK projection), the IV starting dose will be the projected [CCI](#) to the SC starting dose described above, provided that any dose limiting safety events observed in the clinical study following SC dosing are related to local SC injection (eg, skin toxicity at the local SC injection site) but not due to systemic exposure.

4.3.2. Criteria for Dose Escalation

In part 1, a 2-parameter BLRM guided by the EWOC principle will be used to model the dose-DLT relationship of PF-07209960 and guide the dose escalation. Using DLT data at all tested dose levels and pre-specified prior distribution of model parameters, the posterior distribution for probability of having a DLT falling into three dosing intervals (underdosing, target dosing, overdosing) will be calculated for all dose levels. A dose may only be used for newly enrolled participants if the risk of overdosing, ie, toxicity higher than 0.33 at that dose is less than 25%.

Initially, dose escalation increases will be limited to no more than a half log increase from the previous dose level, which is a common approach for biologic compounds ([Saber et al](#),

2016; Saber et al, 2017). Following the observation of a DLT in the current cohort, subsequent dose escalation increases will be limited to no more than 100%. A return to half log dose increases may be permitted at the discretion of the sponsor, in consultation with the participating investigators, if no DLT are seen at the following dose level.

The provisional dose levels to be evaluated are listed in Table 2.

Table 2. Provisional Dose Levels

Dose Level	SC	IV infusion
1		
2		
3		
4		
5		
6		
7		
8		
9		
10		
11		
12		
13		
14		
15		
16		
17		
18		
19		
20		
21		
22		
23		
24		
25		
26		
27		
28		
29		
30		
31		
32		
33		
34		
35		
36		
37		
38		
39		
40		
41		
42		
43		
44		
45		
46		
47		
48		
49		
50		
51		
52		
53		
54		
55		
56		
57		
58		
59		
60		
61		
62		
63		
64		
65		
66		
67		
68		
69		
70		
71		
72		
73		
74		
75		
76		
77		
78		
79		
80		
81		
82		
83		
84		
85		
86		
87		
88		
89		
90		
91		
92		
93		
94		
95		
96		
97		
98		
99		
100		
101		
102		
103		
104		
105		
106		
107		
108		
109		
110		
111		
112		
113		
114		
115		
116		
117		
118		
119		
120		
121		
122		
123		
124		
125		
126		
127		
128		
129		
130		
131		
132		
133		
134		
135		
136		
137		
138		
139		
140		
141		
142		
143		
144		
145		
146		
147		
148		
149		
150		
151		
152		
153		
154		
155		
156		
157		
158		
159		
160		
161		
162		
163		
164		
165		
166		
167		
168		
169		
170		
171		
172		
173		
174		
175		
176		
177		
178		
179		
180		
181		
182		
183		
184		
185		
186		
187		
188		
189		
190		
191		
192		
193		
194		
195		
196		
197		
198		
199		
200		
201		
202		
203		
204		
205		
206		
207		
208		
209		
210		
211		
212		
213		
214		
215		
216		
217		
218		
219		
220		
221		
222		
223		
224		
225		
226		
227		
228		
229		
230		
231		
232		
233		
234		
235		
236		
237		
238		
239		
240		
241		
242		
243		
244		
245		
246		
247		
248		
249		
250		
251		
252		
253		
254		
255		
256		
257		
258		
259		
260		
261		
262		
263		
264		
265		
266		
267		
268		
269		
270		
271		
272		
273		
274		
275		
276		
277		
278		
279		
280		
281		
282		
283		
284		
285		
286		
287		
288		
289		
290		
291		
292		
293		
294		
295		
296		
297		
298		
299		
300		
301		
302		
303		
304		
305		
306		
307		
308		
309		
310		
311		
312		
313		
314		
315		
316		
317		
318		
319		
320		
321		
322		
323		
324		
325		
326		
327		
328		
329		
330		
331		
332		
333		
334		
335		
336		
337		
338		
339		
340		
341		
342		
343		
344		
345		
346		
347		
348		
349		
350		
351		
352		
353		
354		
355		
356		
357		
358		
359		
360		
361		
362		
363		
364		
365		
366		
367		
368		
369		
370		
371		
372		
373		
374		
375		
376		
377		
378		
379		
380		
381		
382		
383		
384		
385		
386		
387		
388		
389		
390		
391		
392		
393		
394		
395		
396		
397		
398		
399		
400		
401		
402		
403		
404		
405		
406		
407		
408		
409		
410		
411		
412		
413		
414		
415		
416		
417		
418		
419		
420		
421		
422		
423		
424		
425		
426		
427		
428		
429		
430		
431		
432		
433		
434		
435		
436		
437		
438		
439		
440		
441		
442		
443		
444		
445		
446		
447		
448		
449		
450		
451		
452		
453		
454		
455		
456		
457		
458		
459		
460		
461		
462		
463		
464		
465		
466		
467		
468		
469		
470		
471		
472		
473		
474		
475		
476		
477		
478		
479		
480		
481		
482		
483		
484		
485		
486		
487		
488		
489		
490		
491		
492		
493		
494		
495		
496		
497		
498		
499		
500		
501		
502		
503		
504		
505		
506		
507		
508		
509		
510		
511		
512		
513		
514		
515		
516		
517		
518		
519		
520		
521		
522		
523		
524		
525		
526		
527		
528		
529		
530		
531		
532		
533		
534		
535		
536		
537		
538		
539		
540		
541		
542		
543		
544		
545		
54		

4.3.3. Dose Limiting Toxicity Definition

For the purpose of dose escalation, any of the following AEs will be classified as DLTs:

- Occur in the first cycle of treatment, or within 28 days after the start of the study treatment; and
- Are at least possibly related to PF-07209960; A participant is classified as DLT evaluable if he/she experiences a DLT or if he/she otherwise in the absence of a DLT receives 2 doses of the study intervention during Cycle 1 and has received all scheduled safety assessments during the DLT window. If a participant fails to meet these criteria, he/she may be replaced. Monitoring for DLTs will occur during Part 1.

Significant AEs considered to be related to the study intervention or treatment under investigation that occur after the DLT observation period will be reviewed in context of all safety data available. That review may result in re-evaluation of the dosing level or regimen.

Hematologic DLTs:

1. Grade 4 neutropenia (absolute neutrophil count [ANC] <500/mm³) lasting >7 days;
2. Febrile neutropenia (defined as an ANC <1000/mm³, with a single temperature of >38.3°C [101°F], or a sustained temperature of ≥38°C [100.4°F] for more than one hour);
3. Neutropenic infection (defined as an ANC <1000/mm³ with Grade ≥3 infection);
4. Grade 3 thrombocytopenia (platelet count <50,000 mm³) with any bleeding;
5. Grade 4 thrombocytopenia (platelet count <25,000/mm³);
6. Grade 4 anemia (life-threatening consequences; urgent intervention indicated).

Non-Hematologic DLTs:

- Any Grade ≥3 non-hematologic treatment related AE is a DLT with the following exceptions:
 1. Grade 3 nausea, vomiting, diarrhea, or fatigue that can be controlled with or without medical therapy to Grade ≤2 within 72 hours;
 2. Grade ≥3 laboratory abnormalities without a clinical correlate and that do not require medical intervention, or are corrected to Grade ≤2 with supplementation/appropriate management within 72 hours;

Immune-related AE (irAE) that meet the following criteria:

1. Grade 4 irAE regardless of duration (for lab abnormalities without clinical correlate and do not require medical intervention please refer to criteria above);

2. Grade ≥ 3 colitis regardless of duration (diagnosis of colitis must be supported by diagnostic testing);
3. Grade ≥ 3 non-infectious pneumonitis regardless of duration;
4. Grade 2 non-infectious pneumonitis that does not resolve to \leq Grade 1 within 72 hours of the initiation of maximal supportive care;
5. Any grade immune-mediated myocarditis;
6. Grade 3 irAE, excluding colitis and pneumonitis, that does not improve to \leq Grade 2 within 72 hours after onset of the AE event despite maximal supportive care including systemic corticosteroids or downgrade to \leq Grade 1 or baseline within 14 days;
7. Grade ≥ 3 immune-related endocrinopathies (eg, thyroid disorders, diabetes mellitus, adrenal insufficiency) that require treatment discontinuation or are not successfully managed with hormonal replacement therapy.

Other cases that meet the following DLT criteria:

1. Hy's Law cases defined as: ALT or AST $>3 \times$ ULN if normal at baseline OR $>3 \times$ ULN and doubling the baseline (if $>$ ULN at baseline) associated with total bilirubin $>2 \times$ ULN and an alkaline phosphatase $<2 \times$ ULN.
2. A treatment related AE inducing a delay by ≥ 4 weeks in receiving the next scheduled cycle due to persisting toxicities attributable to PF-07209960 will be considered a DLT.
3. Clinically important or persistent toxicities (eg, toxicities responsible for significant dose delay) that are not included in the above criteria may also be considered a DLT following review by the investigators and the sponsor. All DLTs need to represent a clinically significant shift from baseline. While the rules for adjudicating DLTs are specified above, an AE not listed above, or an AE meeting the DLT criteria above but occurring outside of the DLT observation period may be defined as a DLT following assessment, based on the emerging safety profile.

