9.3. Analysis Sets

1. Full analysis set.

The full analysis set includes all enrolled participants.

"Enrolled" means a participant's, or their legally authorized representative's, agreement to participate in a clinical study following completion of the informed consent process. Potential participants who are screened for the purpose of determining eligibility for the study, but do not participate in the study, are not considered enrolled, unless otherwise specified by the protocol.

2. Safety analysis set.

The safety analysis set includes all enrolled participants who receive at least one dose of study intervention. Unless otherwise specified, the safety analysis set will be the default analysis set used for all analyses.

3. Per protocol analysis set (evaluable for MTD).

The per protocol analysis set includes all enrolled and evaluable participants who had at least one dose of study treatment and either experienced DLT or do not have major treatment deviations during the DLT observation period.

4. mITT Population.

The mITT is the analysis population that will follow the ITT principle and include participants receiving at least 1 dose of study medication with baseline assessment and at least 1 post baseline assessment, disease progression, or death before the first tumor assessment. The mITT population may be used for interim analysis and conference presentations when the study is still ongoing.

5. PK analysis sets.

The PK parameter analysis population is defined as all enrolled participants treated who do not have protocol deviations influencing PK assessment, and have sufficient information to estimate at least 1 of the PK parameters of interest.

The PK concentration population is defined as all enrolled participants who are treated and have at least 1 postdose analyte concentration.

6. Response Evaluable Set.

The response evaluable population will include all participants who received at least one dose of study treatment and had baseline disease assessment and at least one post baseline disease assessment.

7. PD/Biomarker analysis set(s).

The PD/Biomarker analysis population is defined as all enrolled participants with at least 1 of the PD/Biomarkers evaluated at pre and/or post dose.

8. Immunogenicity analysis set.

The immunogenicity analysis set includes all enrolled participants who receive at least one dose of study treatment and have at least one sample tested for ADA.

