9.4.1. Maximum Tolerated Dose Determination

Determination of MTD will be performed using per protocol analysis set (evaluable for MTD).

Bayesian adaptive approach:

The dose escalation in the Part 1 of the study will be guided by a Bayesian analysis of DLT data for PF-07209960. Dose toxicity is modelled using two-parameter logistic regression for the probability of a participant experiencing a DLT at the given dose.

Assessment of Participant Risk:

After each cohort of participants, the posterior distribution for the risk of DLT for new participants at different doses of interest for PF-07209960 will be evaluated. The posterior distributions will be summarized to provide the posterior probability that the risk of DLT lies within the following intervals:

Under-dosing	[0, 0.16]
Targeted dosing	[0.16, 0.33]
Overdosing	[0.33, 1]

The EWOC principle:

Dosing decisions are guided by the escalation with overdose control principle ([Rogatko et al, 2007](#)). A dose may only be used for newly enrolled participants if the probability of overdosing at that dose is **CCI**.

Recommendation from the BLRM, along with safety (AEs, SAEs), laboratory, PK, biomarker and other relevant data, will be used at the time of each dose escalation and for MTD/RP2D determination.

Prior distributions:

Weakly informative prior distributions based on pre-clinical/expert opinion information will be chosen for the logistic parameters, see [Appendix 8](#).

Starting dose:

The starting dose is **CCI** in Part 1 Dose Escalation. For this dose the prior risk of overdosing satisfies the EWOC criterion.

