4. ANALYSIS SETS (POPULATIONS FOR ANALYSIS)

Data for all participants will be assessed to determine if participants meet the criteria for inclusion in each analysis population prior to unblinding and releasing the database and classifications will be documented per standard operating procedures.

Table 2. Analysis Sets

Population	Description
Full analysis set	The full analysis set includes all enrolled participants. "Enrolled" means a participant's, or their legally authorized representative's, agreement to participate in a clinical study following completion of the informed consent process. Potential participants who are screened for the purpose of determining eligibility for the study, but do not participate in the study, are not considered enrolled, unless otherwise specified by the protocol.
Safety analysis set	The safety analysis set includes all enrolled participants who receive at least one dose of study intervention. Unless otherwise specified the safety analysis set will be the default analysis set used for all analyses.
Per protocol analysis set (Evaluable for MTD)	The per protocol analysis set includes all enrolled participants who had at least one dose of study treatment and either experienced DLT or do not have major treatment deviations during the DLT observation period. To be DLT evaluable, a participant must have received at least 75% of their planned doses in each cycle for the first two cycles (i.e., ≥ 11 doses received in each of the first two cycles) and has received all scheduled safety assessments during the DLT window.
Modified Intent to Treat (mITT)	The modified intent to treat (mITT) is the analysis population that will follow the ITT principle and include participants receiving at least 1 dose of study medication with baseline assessment and at least 1 post baseline assessment, disease progression, or death before the first tumor assessment. The mITT population may be used for interim analysis and conference presentations when the study is still ongoing.
PK analysis sets	The PK parameter analysis population is defined as all enrolled participants treated who do not have protocol deviations influencing PK assessment, and have sufficient information to estimate at least 1 of the PK parameters of interest.

Population	Description

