6.1.1. Dose-Limiting Toxicities (DLTs)

- Analysis set: Per protocol analysis set
- Analysis methodology:

For the purpose of dose escalation, the DLT observation period/window will be the first cycle (defined as 28 days after the start of study treatment), for each participant. Whether an adverse event a participant experienced during the DLT window is determined as a DLT or not is based on the DLT definitions provided in Section 4.3.3 of the protocol.

The DLT events will be summarized by dose level. A listing of the DLT events will also be provided in which the participant's primary diagnosis (malignancy), dose level the participant was enrolled to, DLT event start day and stop day relative to the C1D1 dose date, the DLT event term, NCI CTCAE grade, relatedness to the investigational product (PF-07209960), outcome of the event, along with other variables deemed important, will be included.

- Missing data: All enrolled participants in Part 1 should have an indicator variable derived to be either 1 (yes) or 0 (no) based on the DLT definitions (provided in

Section 4.3.3 of the protocol) and participant's safety data during the DLT observation window. If a participant fails to have a value on the indicator variable because the participant being non-DLT-evaluable, the participant may be replaced.

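### One missed Cycle 1 safety assessment, of any kind, removes a DLT-free participant from the MTD analysis but not one with a DLT (Protocol 4.3.3); unless missed assessments hide DLTs at least as often, this modestly raises the observed DLT rate

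*Protocol*

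**What the plan says.** Protocol 4.3.3 offers two routes to evaluability: "he/she experiences a DLT or if he/she otherwise in the absence of a DLT receives 2 doses of the study intervention during Cycle 1". For the DLT-free route it sets a further condition: "has received all scheduled safety assessments during the DLT window". It gives no tolerance and no list of the assessments that matter. It then adds: "If a participant fails to meet these criteria, he/she may be replaced".

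Protocol 9.4.1 states: "Determination of MTD will be performed using per protocol analysis set". Protocol 9.3 builds that set from "all enrolled and evaluable participants who had at least one dose of study treatment" who "either experienced DLT or do not have major treatment deviations during the DLT observation period". The word evaluable leads back to 4.3.3, but the only exclusion named in 9.3 concerns treatment deviations, not missed assessments.

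SAP Table 2 keeps participants who had a DLT in its first sentence. Its next sentence defines DLT evaluable without repeating that exemption. It repeats the all-assessments condition and adds that the participant must have "received at least 75% of their planned doses in each cycle for the first two cycles", glossed as at least 11 doses per cycle. SAP 6.1.1 expects a yes/no DLT indicator for every enrolled Part 1 participant, but also foresees a missing value "because the participant being non-DLT-evaluable, the participant may be replaced".

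**The concern.** Under 4.3.3, exclusion depends on the outcome. The numerator of the DLT rate is kept whole, while the denominator can lose DLT-free participants for reasons unrelated to toxicity. The condition reaches beyond what is needed to rule out a DLT: urinalysis and ECOG status are scheduled in Cycle 1, but no listed DLT criterion names either.

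Missed tests are expected. Protocol 8 accepts that required tests will sometimes be unfeasible. Protocol Appendix 10 permits telehealth visits whose mandatory content does not include a physical examination or vital signs.

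Nothing later in the plan corrects for the exclusion. Protocol 9.6 describes the dose review as choosing the model's recommended dose or a lower one. The only planned BLRM sensitivity analysis (Protocol 9.4.1.1 and Appendix 8) concerns equivocal DLTs. At stake are the DLT rate fed to the BLRM, the selected MTD, and the use made of a small Part 1 sample.

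**Working it through.** No stated figure in the plan depends on this rule, so there is none to reproduce. The 14-22 participants for Part 1 come without a formula, and the operating characteristics are in a technical supplement that is not part of these documents.

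**Inputs.** From the documents: target interval 0.16 to 0.33 (Protocol 4.3.4); a dose is usable only if the probability that its DLT rate exceeds 0.33 is below 25% (Protocol 4.3.2); at least 6 participants at the MTD (Protocol 9.2.1 and 9.4.1.1). Assumed:
- p: the true DLT rate.
- m: the share of DLT-free participants excluded for a missed assessment.
- h: the share of would-be DLT participants whose DLT goes unseen and who are excluded.

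**Formula.** Expected observed rate = p(1−h) / [p(1−h) + (1−p)(1−m)]. It exceeds p if and only if h < m.

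**Largest upward shift (h = 0, every DLT seen).** For example, with p = 0.25 and m = 10%: 0.25 / (0.25 + 0.75 × 0.90) = 0.25 / 0.925 = 0.270.

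| True rate | m = 5% | m = 10% | m = 20% | m = 30% |
|---|---|---|---|---|
| 0.25 | 0.260 | 0.270 | 0.294 | 0.323 |
| 0.30 | 0.311 | 0.323 | 0.349 | 0.380 |

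**Exclusion needed to reach 0.33.** m = 1 − (p/0.33 − p)/(1 − p), which gives 32% for p = 0.25, 13% for p = 0.30 and 4.5% for p = 0.32.

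**Direction.** At p = 0.25 and m = 10%, h = 5% gives 0.260 (up), h = 10% gives 0.250 (no bias) and h = 20% gives 0.229 (down).

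**Sampling error for scale.** With 6 participants at a true 0.25, the standard error is √(0.25 × 0.75 / 6) = 0.177. A shift of 0.01 to 0.02 is small beside it, but it is systematic and does not average out.

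**Effect on dose selection (illustration only).** A two-parameter BLRM was simulated 3,000 times per setting with cohorts of three, the 25% overdose limit, the plan's stopping rule, every excluded participant replaced, and h = 0. The prior, the six dose levels and the DLT curves are assumptions. Monte Carlo error is about 0.9 percentage points.

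| m | 0 | 5% | 10% | 20% | 30% |
|---|---|---|---|---|---|
| Curve A (.02/.05/.12/.25/.40/.55): below-target dose selected | 63% | 66% | 68% | 73% | 77% |
| Curve A: target dose selected | 23% | 21% | 20% | 17% | 13% |
| Curve A: mean number enrolled | 16.9 | 17.4 | 18.0 | 19.7 | 21.8 |
| Curve B (.01/.03/.08/.18/.30/.45): below-target dose selected | 47% | 49% | 51% | 57% | 62% |

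**Consistency of the definitions.** Treatment is given on Days 1 and 15 of a 28-day cycle, which is two doses per cycle, and the DLT window is 28 days. A condition of at least 11 doses in each of two cycles cannot be met on that schedule and extends past the window.

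**The case against.** Some asymmetry is inherent in any DLT-evaluable definition: a participant with a real gap in observation cannot be called DLT-free. That stands. Dropping the requirement altogether would create the opposite bias. If a share h of DLTs goes unseen and those participants count as DLT-free, the rate reads p(1−h), so a true 0.25 becomes 0.225 at h = 10% and 0.200 at h = 20%.

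The direction is also conditional. Many DLTs (platelets, neutrophils, Hy's Law chemistry) are found by the scheduled tests themselves, so a missed test can hide one. Against that, hematology, chemistry and AE checks recur through Cycle 1, which makes h ≥ m less likely, though the documents do not settle it.

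A reader might infer a much larger effect by counting about 50 scheduled Cycle 1 safety assessments and treating them as independent. Completion of 0.995, 0.99 or 0.98 each would make a true 0.25 read 0.30, 0.36 or 0.48. The documents do not support this. The assessments cluster in seven visits (Days 1, 2, 3, 4, 8, 15 and 22). Four of these fall at or during the 72-hour inpatient stay, and Day 15 is the second dose, already required for evaluability. Applying the same three probabilities per visit, 0.995^7, 0.99^7 and 0.98^7 give 0.966, 0.932 and 0.868 of DLT-free participants kept, and a true 0.25 reads 0.257, 0.263 or 0.277. The per-visit figures are assumptions too.

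Two further points stand in part. The operative limit is a posterior probability, not a point rate against 0.33, and the illustrative model already favors low doses when nothing is missing. The sample-size cost is partly foreseen, since Protocol 9.2.1 lets the Part 1 total depend on how many participants are evaluable.

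**Conclusion.** The point holds in conditional and modest form. Protocol 4.3.3 excludes DLT-free participants for missed assessments that may have no bearing on a DLT and keeps all participants with one. Where h < m, this raises the observed rate and shifts selection toward lower doses. With all DLTs seen and 5% to 20% of DLT-free participants excluded, a true 0.25 reads 0.26 to 0.29. The shift matters chiefly when the true rate is already close to 0.33 or missingness is heavy. These sizes rest on assumed values of m and h.

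A reader might also infer that a DLT always secures inclusion. Protocol 4.3.3 and 9.3 say so, but the SAP's evaluability sentence omits the exemption. Until the three definitions are reconciled, membership of the primary Part 1 set cannot be stated with certainty.

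**What to change.** 1. In Protocol 4.3.3, leave the Cycle 1 dosing condition as it is. Replace the all-assessments condition with completed follow-up to the end of the DLT window plus a prespecified list of DLT-relevant assessments (AE review, hematology, chemistry) sufficient to rule out a DLT. Participants with a real gap in those stay non-evaluable; other missed assessments are recorded as deviations.
2. Confirm each participant's evaluability at the dose level review before the BLRM is run.
3. Run the BLRM once as a sensitivity analysis that includes DLT-free participants excluded only for missed assessments. Because it counts them all as DLT-free, it can understate the rate if a DLT was hidden, so read it alongside the main run.
4. Use this one definition, with the DLT exemption stated, in Protocol 4.3.3, Protocol 9.3 and SAP Table 2.
5. Reconcile the SAP's two-cycle, 11-dose condition with the 28-day DLT window and the Day 1 and Day 15 schedule.

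The cost is short edits in three places, one more model run, and an item at a meeting already planned. The small downside is some judgement about what counts as sufficient data, in an open-label review whose data may be unqueried (Protocol 9.6). The prespecified list limits it.
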